**Table 5-1 Prohibited treatment**

Medication	Action to be taken
Anti-VEGF drugs other than ranibizumab (ocular or systemic)	Withdraw patient from study
Intra- or periocular corticosteroids (including sub-tenon but excluding topical formulations) – study eye only	Withdraw patient from study
Intra-ocular corticosteroid implants – study eye only	Withdraw patient from study
Investigational drugs and interventions of any type	Withdraw patient from study

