### 5.5.9 Discontinuation of study treatment

Patients may voluntarily discontinue study treatment for any reason at any time.

The study and treatment completion dates will be determined by the last visit the patient came to the clinic.

The Investigator must provide follow-up medical care for all patients who are prematurely withdrawn from the study, or must refer them for appropriate ongoing care. Patients who are prematurely withdrawn from the study will not be replaced by an equal number of newly enrolled patients.

Patients can discontinue study treatment because of the appearance of a new health condition suspected to require appropriate care or require medications prohibited by the protocol (Section 5.5.8), unacceptable AEs, refusal to continue treatment, or at the Investigator's discretion based on his or her clinical judgment.

The Investigator should discontinue study treatment for a given patient or withdraw the patient from study if, on balance, he/she believes that continuation would be detrimental to the patient's well-being.

Study treatment must be discontinued under the following circumstances:

- Withdrawal of informed consent
- Emergence of the following AEs:
  - Stage 3 or 4 macular hole
  - Stroke or transient ischemic attack
  - Rhegmatogenous retinal detachment
- Pregnancy
- Use of prohibited treatment in Table 5-1
- Two sequential ranibizumab injections to the study eye should have occurred according to the protocol specified monthly/PRN treatment period criteria but were withheld (see Section 5.5.5) or missed.

- Any other protocol deviation that results in a significant risk to the patient's safety.

Patients who permanently discontinue study treatment and start a prohibited non-study treatment (see Section 5.5.8) should be withdrawn from the study and undergo all assessments for End of Study visit as described in Table 6-1 and Table 6-2.

Patients who discontinue study treatment but do not receive prohibited treatment should not be considered withdrawn from the study and may continue their scheduled follow-up assessments until End of Study.

The Completion/Withdrawal eCRF page should be completed, providing the primary reason for stopping study treatment.

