**Table 6-1 Assessment schedule (Eligibility criteria, demographics & baseline characteristics, imaging procedures)**

	Screening V1	Baseline V2	V3	V4	PEV V5	V6	V7	EOS or EWV V8	UNSCHED V
Days relative to Day 1 (permitted time window)	Primary treatment failure≤40 days Suboptimal treatment response≤70 days prior to Baseline visit	1	30±7	60±7	90±7	120±7	150±7	180±7	
Informed consent	X								
Review of inclusion/exclusion criteria	X	X							
Diagnosis	X								
Demography	X								
Medical History	X	X							
Prior/concomitant meds	X	X	X	X	X	X	X	X	X
Serum pregnancy test	X								
BCVA score (ETDRS)	X*	X*	X	X	X*	X	X	X*	X*
Historical retinal images collected	X								
Ophthalmic examination	X	X	X	X	X	X	X	X	
OCT (retina and choroid)	X	X	X	X	X	X	X	X	
Color fundus photography	X							X	
Fluorescein angiography	X							X	
Fundus autofluorescence	X							X	
Indocyanine green angiography	X								
PEV: Primary Endpoint Visit. EOS: End of Study visit also incorporates the Early Withdrawal Visit (EWV). UNSCHED V: Unscheduled visit * Assessment to be performed also on fellow-eye; where ranibizumab treatment is initiated in the fellow-eye BCVA is to be repeated and recorded in the eCRF prior to injection.									

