### 9.1 Analysis sets

For all patients only one eye will be considered as the study eye, but efficacy and safety parameters will be recorded for both eyes. In the event that a subject develops visual impairment due to nAMD in the fellow eye (non-study eye) during the study which is treated at the Investigator's discretion according to the standard of care, any additional data (except for BCVA, ranibizumab injections and AEs and SAEs that occur in the fellow eye) collected according to routine practice will not be recorded on the eCRF. Data presentations will distinguish study and fellow eye values.

The **Full Analysis Set (FAS)** will consist of all patients who received at least one application of study treatment in the study eye, have baseline and have at least one post-baseline assessment for CSRT. Following the intent-to-treat principle, patients will be analyzed according to the treatment assigned. No data will be excluded from the FAS analyses because of protocol deviations.

The **Per Protocol Set (PPS)** will consist of all patients in the FAS who followed the assigned treatment and completed the study without clinically significant protocol deviations. Clinically significant protocol deviations will be defined in the Statistical Analysis Plan. If deviations do occur, then the data from specific patients, visits, or evaluations may be excluded from the PPS. The criteria and determination of clinically relevant protocol deviations and patient specific identification of data to be excluded from the PPS will be databased and finalized prior to database lock.

The **Safety Set (SAF)** will consist of all patients who received at least one application of study treatment in the study eye and had at least one post-baseline safety assessment. The statement that a patient had no adverse events also constitutes a safety assessment.

All efficacy evaluations will be carried out on the Full Analysis Set and all safety evaluations will be carried out on the Safety Set.

For sensitivity purposes, the primary analysis will be repeated using the Per Protocol Set. Any major discrepancies in the results across analyses will be investigated as necessary.

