### **9.4.3 Handling of missing values/censoring/discontinuations**

In the event that CSRT is missing for Day 90, the analysis will follow an LOCF (Last Observation Carried Forward) approach for the Full Analysis Set. This will only be done for the primary outcome.

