2.1.3 Protocol deviations

Protocol deviations (PDs) are collected as per the latest version of the VAP Module 3 - Protocol Deviations (see Appendix 2). This document gives a full list of possible PDs, including whether they are programmatically or manually derived, as well as Severity/Analysis classification codes to be assigned to each PD. Rules for patient classification in the analysis sets based on PDs are as follows:

Protocol deviations and impact on analysis

Code	VAP de-code	Impact on analyses
0	Exclude from all efficacy analysis (including ITT)	Exclude patient completely from the FAS and Per-Protocol Sets.
1	Exclude from Per-Protocol analysis	Exclude patient completely from Per-Protocol Set.
2	Exclude from data analysis from this date	Data from this date/visit onwards excluded from per protocol analyses (patient not excluded from population).

49 Report relevant protocol deviation – Include in all analysis
include in all analyses

A protocol deviation meeting will be organized. The criteria and determination of clinically relevant protocol deviations and patient specific identification of data to be excluded from the PPS following this meeting will be databased and finalized prior to database lock.

All protocol deviations will be listed. All responses to the screening and baseline log will also be listed.

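### An early-withdrawal OCT that may follow a prohibited drug is not barred from being carried forward to Day 90 in the primary CSRT analysis

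*Protocol*

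**What the plan says.** **Trigger.** Protocol 5.5.9 directs that patients who permanently stop ranibizumab and "start a prohibited non-study treatment (see Section 5.5.8) should be withdrawn from the study and undergo all assessments for End of Study visit". The same section lists "Use of prohibited treatment in Table 5-1" among the events that force study treatment to stop. It treats the other group differently: "Patients who discontinue study treatment but do not receive prohibited treatment should not be considered withdrawn from the study", and these patients may stay on scheduled visits.

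**Treatments that count.** Table 5-1 covers anti-VEGF drugs other than ranibizumab (ocular or systemic), intra- or periocular steroids and steroid implants in the study eye, and investigational drugs or interventions of any kind. The action for each is withdrawal.

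**The scan.** In Table 6-1 the End of Study column also serves as the early-withdrawal visit, and OCT is marked there.

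**Missing Day 90.** For a missing Day 90 CSRT, protocol 9.4.3 says "the analysis will follow an LOCF (Last Observation Carried Forward) approach for the Full Analysis Set". SAP 2.2.1.2 repeats the rule. Neither says which observations may be carried.

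**Data exclusions.** Protocol 9.1 and SAP 2.1.1 state: "No data will be excluded from the FAS analyses because of protocol deviations". In SAP 2.1.3, code 2 means "Data from this date/visit onwards excluded from per protocol analyses". Code 0 in the same table removes a patient entirely from both the FAS and the Per Protocol Set (PPS).

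**The concern.** The primary objective is the change in CSRT after three monthly ranibizumab injections. A scan read after another anti-VEGF drug or a study-eye steroid does not measure that. Under 5.5.9, stopping ranibizumab does not by itself prompt the withdrawal visit; starting the other treatment does. The scan may therefore come after the drug whose effect it ought to exclude.

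If this happens before a Day 90 OCT, the withdrawal scan can be the last observation on file and so the one carried to Day 90. Investigators may stop treatment on clinical judgment, so patients moved to another drug this early could include some who did poorly on ranibizumab. Any fall in CSRT on the new drug would then be credited to ranibizumab, and there is no comparator arm to offset it.

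The point is which scan LOCF may carry. It is not an objection to LOCF as such.

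**Working it through.** **Step 1. Follow the text for a patient who starts a prohibited treatment before Day 90.**

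1. The start of that treatment leads to withdrawal and the End of Study assessments (5.5.9, Table 5-1).
2. Those assessments include OCT (Table 6-1).
3. No rule places that OCT before the prohibited treatment. The requirement to assess before dosing, in protocol 6.4 under study eye selection, covers ranibizumab only.
4. The patient is withdrawn, so no Day 90 CSRT is collected.
5. LOCF fills Day 90 in the FAS, with no stated limit on the source scan (9.4.3, SAP 2.2.1.2).
6. The FAS keeps data despite deviations, and the only cut by date (code 2) acts on per-protocol analyses.

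One post-baseline CSRT is enough for FAS membership, so a patient could enter the FAS on this scan alone.

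**Step 2. Check the plan's figures used below.** The Amendment 2 summary gives an SD of differences of 102 µm (previously 117) and N = 124 (previously 162). Effect size and power are not in the public copy, so N cannot be fully reproduced. Since N scales with SD², 162 × (102/117)² = 123.1, which agrees with 124. An assumed effect of 30 µm with 90% power in a two-sided 0.05 paired t-test gives 124 and 162 exactly. The point does not depend on that assumption.

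**Step 3. Size of the shift.** Let m be the number of FAS patients whose carried scan follows a prohibited treatment, and s the CSRT fall that treatment caused. Both are assumptions; no document gives either.

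- Shift in the mean = m × s / 124.
- Standard error = 102/√124 = 9.16 µm.
- If the true mean change is zero, the chance that a two-sided 0.05 test shows a significant reduction is about Φ(−1.96 + shift/SE). With no shift it is 0.025.

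| m | s (µm) | Shift toward benefit (µm) | Shift/SE | Chance of false reduction |
|---|---|---|---|---|
| 3 | 50 | 3×50/124 = 1.2 | 0.13 | 0.034 |
| 3 | 100 | 3×100/124 = 2.4 | 0.26 | 0.045 |
| 6 | 50 | 6×50/124 = 2.4 | 0.26 | 0.045 |
| 6 | 100 | 6×100/124 = 4.8 | 0.53 | 0.076 |

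Over a wider range the shift runs from 1×50/124 = 0.4 µm (0.04 SE) to 12×150/124 = 14.5 µm (1.6 SE). Nothing in the documents suggests that the upper end is realistic.

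**The case against.** **Order of drug and scan.** A reader might infer that the withdrawal scan always follows the other drug. The documents do not support that. Section 5.5.9 fixes no order or interval, and it lets a patient stop because a prohibited medication is expected to be needed, or be withdrawn on the investigator's judgment. A site could scan first. What stands is that nothing requires this, and the stated trigger is the start of the drug.

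**Code 0.** It could take such a patient out of the FAS. The list of deviations that carry this code (SAP Appendix 2) is not shown, so this cannot be ruled out. It would contradict the FAS sentence and would also discard valid earlier scans.

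**Unseen text.** Neither LOCF passage names the early-withdrawal visit or says how its readings are assigned to analysis visits, and parts of both analysis sections are missing from the public copy. The claim is therefore limited to the absence of a visible rule.

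**Direction.** A reader might infer that the bias always favours ranibizumab, or that every such patient is a ranibizumab failure. Table 5-1 also covers systemic, fellow-eye and investigational treatments that need not change study-eye CSRT. A scan soon after a switch may still show worsening. All patients entered with inadequate control on aflibercept, so a large fall on returning to it is not established.

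**PPS and intent-to-treat.** The PPS requires study completion, so it omits these patients, but it is only a sensitivity analysis and leaves the primary result unchanged. The intent-to-treat label does not settle the matter either. An observed Day 90 value regardless of treatment would fit that principle, but these patients are withdrawn. The carried scan is neither a value on ranibizumab alone nor an observed Day 90 value.

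**Conclusion.** The gap is real but conditional. For a patient who starts a prohibited treatment before a Day 90 OCT, the withdrawal scan may be read under that treatment, and no visible rule keeps it out of the primary FAS result. A withdrawal after the Day 90 scan does no harm, because the Day 90 value is then observed.

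The size is unknown. Under the assumed 3 to 6 patients and 50 to 100 µm, the shift is about 0.1 to 0.5 SE. That is small for the estimate, though at the top of that range the one-sided error would be about three times nominal (0.076 against 0.025). With fewer patients, early scans or drugs acting elsewhere, the effect may be close to nil. The documents do not support calling the primary result biased; they support calling the carry-forward rule incomplete. This is a cheap improvement worth making before database lock.

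**What to change.** 1. In protocol 9.4.3 and SAP 2.2.1.2, define the value carried forward as the last post-baseline CSRT acquired before the first Table 5-1 treatment. List later scans, but do not carry them forward.
2. State how a patient with no earlier post-baseline scan is handled, including whether a scan taken after the prohibited treatment is enough for FAS membership.
3. Align this rule with the FAS sentence in protocol 9.1 and SAP 2.1.1, and say whether code 0 is meant to apply to prohibited treatment.
4. Record in the eCRF whether the early-withdrawal OCT came before or after the prohibited treatment, including when both fall on the same day. The SAP's medication listing has start and end dates but no times, so dates alone cannot settle same-day cases.

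The cost is a few sentences in the protocol and SAP and one eCRF item. The downside is that a few patients will carry forward an older scan, from Day 30 or Day 60. The change concerns data eligibility and recording only; it does not touch when or whether any non-study treatment is given.

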### **5.5.10 Withdrawal of consent**

Patients may voluntarily withdraw consent to participate in the study for any reason at any time.

Withdrawal of consent occurs only when a patient does not want to participate in the study anymore and does not want any further visits or assessments and does not want any further study related contacts and does not allow analysis of already obtained biologic material.

If a patient withdraws consent, the Investigator must make every effort (e.g. telephone, e-mail, letter) to determine the primary reason for this decision and record this information in the eCRF. Study treatment must be discontinued and no further assessments conducted. All biological material that has not been analyzed at the time of withdrawal must not be used. Further attempts to contact the patient are not allowed unless safety findings require communicating or follow-up.

The Completion/Withdrawal eCRF page should be completed, providing the primary reason for stopping study treatment.

### **5.5.11 Loss to follow-up**

For patients who are lost to follow-up (i.e., those patients whose status is unclear because they fail to appear for study visits without stating an intention to withdraw), the Investigator should show due diligence by documenting in the source documents the steps taken to contact the patient (e.g., dates of telephone calls, registered letters).

The Completion/Withdrawal eCRF page should be completed, providing the primary reason for stopping study treatment.

### **5.5.12 Emergency breaking of assigned treatment code**

Not applicable as all patients will receive ranibizumab 0.5mg

### **5.5.13 Study completion and post-study treatment**

Patients who already have entered the Screening Period should not enter the Treatment Period once the planned number of patients has been found eligible to commence treatment in the study.

The Investigator must provide follow-up medical care for all patients who are prematurely withdrawn from the study, or must refer them for appropriate ongoing care.

Patients who successfully complete all study assessments of the study through to Day 180 will be considered to have completed the study.

The study is considered as completed once, according to the study protocol, all protocol required activities have been executed in all treated patients.

No extension study has been planned.

Following completion of the study, all patients will be provided with appropriate ongoing care according to the Investigator's or treating ophthalmologist's judgment.

### **5.5.14 Early study termination**

The study can be terminated at any time and for any reason by Novartis. Should this be necessary, the patient should be seen as soon as possible and treated as described in Section 6 for a prematurely withdrawn patient. The Investigator may be informed of additional procedures to be followed in order to ensure that adequate consideration is given to the protection of the patient's interests. The Investigator will be responsible for informing the local IEC of the early termination of the trial.

## **6 Visit schedule and assessments**

Table 6-1 and Table 6-2 list all the assessments and procedures to be performed by study visits.

All data obtained from these assessments must be supported in the patient's source documentation. Assessments are indicated with an "X" when they need to be performed.

A planned study visit schedule will be established at the time of Baseline visit (Day 1) for all patients. Study assessments will be performed at the Screening visit, Baseline (Day 1), and at Day 30, Day 60, Day 90, Day 120, Day 150 and Day 180,  $\pm 7$  days to allow for flexibility in scheduling. In addition, the Screening visit may be performed over a maximum of 2 consecutive days; if this occurs, the last day must be entered as the visit date in the eCRF

Should a deviation from the study visit schedule occur, all efforts should be made to return to the planned visit schedule taking into consideration the restrictions on the minimum treatment interval between ranibizumab treatments which should be  $\geq 23$  days.

At a minimum, patients will be contacted and reviewed in the clinic for safety evaluations either at Day 180 ( $\pm 7$ ) days, or during the 30 days following the last administration of study treatment. Documentation of attempts to contact the patient should be recorded in the source documentation.

Should unscheduled study visits occur, the Investigator will ask the patient for information regarding the use of concomitant medications and new or ongoing adverse events, which will be recorded in source documentation and in the eCRF. BCVA for both eyes, vital signs and ranibizumab injections that occur at unscheduled study visits will also be recorded in the eCRF.

**Table 6-1 Assessment schedule (Eligibility criteria, demographics & baseline characteristics, imaging procedures)**

	Screening V1	Baseline V2	V3	V4	PEV V5	V6	V7	EOS or EWV V8	UNSCHED V
Days relative to Day 1 (permitted time window)	Primary treatment failure≤40 days Suboptimal treatment response≤70 days prior to Baseline visit	1	30±7	60±7	90±7	120±7	150±7	180±7	
Informed consent	X								
Review of inclusion/exclusion criteria	X	X							
Diagnosis	X								
Demography	X								
Medical History	X	X							
Prior/concomitant meds	X	X	X	X	X	X	X	X	X
Serum pregnancy test	X								
BCVA score (ETDRS)	X*	X*	X	X	X*	X	X	X*	X*
Historical retinal images collected	X								
Ophthalmic examination	X	X	X	X	X	X	X	X	
OCT (retina and choroid)	X	X	X	X	X	X	X	X	
Color fundus photography	X							X	
Fluorescein angiography	X							X	
Fundus autofluorescence	X							X	
Indocyanine green angiography	X								
PEV: Primary Endpoint Visit. EOS: End of Study visit also incorporates the Early Withdrawal Visit (EWV). UNSCHED V: Unscheduled visit * Assessment to be performed also on fellow-eye; where ranibizumab treatment is initiated in the fellow-eye BCVA is to be repeated and recorded in the eCRF prior to injection.									

**Table 6-2 Assessment schedule (peri-injection procedures, safety assessments and venous blood sample collection)**

	Screening V1	Baseline V2	V3	V4	PEV V5	V6	V7	EOS or EWW V8	UNSCHED V
Dispense topical antibiotic medication according to local practice		(X)	(X)	(X)	(X)	(X)	(X)		
Ranibizumab injection		X	X	X	(X)	(X)	(X)		
Post-injection assessments		X	X	X	(X)	(X)	(X)		
Vital signs	X	X	X	X	X	X	X	X	X
Height and Weight	X								
Adverse events	X	X	X	X	X	X	X	X	X
PEV: Primary Endpoint Visit. EOS: End of Study visit also incorporates the Early Withdrawal Visit (EWW). UNSCHED V: Unscheduled visit (X) Indicates that local standard practice should be applied or in the case of ranibizumab injection, that Investigator judgment is used to determine whether repeat injection is required.									

## **6.1 Information to be collected on screening failures**

All patients who have signed informed consent but not initiated study treatment at Baseline will be considered Screen Failures. For these patients demographics, inclusion/exclusion fulfillment, and adverse event (AE) data will be collected. The Completion/Withdrawal page in the eCRF will be completed.

## **6.2 Patient demographics/other baseline characteristics**

Patient demographic and baseline characteristics to be collected on screened patients include:

- Demography: year of birth, gender, race, ethnicity
- Relevant medical history/current medical condition data includes data until the informed consent form is signed. Where possible, diagnoses and not symptoms will be recorded. Investigators will have the discretion to record abnormal test findings on the medical history eCRF whenever the test abnormality occurred before the informed consent signature
- Study eye selection
- Baseline characteristics
- Prior utilization of aflibercept (number and dates of injections into one or both eyes)
- Other assessments performed at Screening to determine eligibility are listed in Table 6-1.

At the Baseline visit and after review of eligibility criteria, patients will be allocated to either the primary treatment failure subgroup or to the suboptimal treatment response subgroup.

